9.5 Analysis of secondary variables

9.5.1 Efficacy variables (Core part)

All efficacy analyses will be done based on the FAS, unless explicitly stated otherwise.

9.5.1.1 Number of new or newly T2 lesions on MRI scans

Analysis of the number of new or enlarging T2 lesions will be done based on the FAS using a negative binomial regression model with log-link. The number of new or enlarging T2 lesions on the last available MRI scan relative to baseline will be used as the response variable, and the natural log of the time (in years) of the MRI-assessment from the baseline/Screening scan will serve as the offset variable to adjust for the various lengths of follow-up times between patients in this study. The model will include treatment, region (Japan or other countries), baseline number of Gd-enhancing T1 weighted lesions (0 or ≥ 1) as factors, and baseline volume of T2 lesions as continuous covariates.

The number of new or enlarging T2 lesions per year will be estimated by treatment with 95% confidence interval. The between treatment effect will be calculated as rate-ratio with 95% confidence interval and p-value. In addition the relative reduction in the number new or enlarging T2 lesions per year will be computed as the rate-ratio minus one (1) and expressed as a percentage.

9.5.1.2 Annualized relapse rate (ARR)

Analysis of ARR will be done based on the FAS, using a negative binomial regression model with log-link, treatment, region (Japan or other countries), baseline number of Gd-enhancing T1 weighted lesions (0 or ≥ 1) as factors, and number of relapses in previous year and baseline EDSS as covariates. In the analysis, the response variable is the number of confirmed relapses observed from each patient and the patient's time in study (natural log of time in years) is used as an offset variable to adjust for the varying lengths of patient's time in the study. The adjusted ARR (i.e., model-based estimate adjusted for covariates) for each treatment and the corresponding 95% confidence interval, and ARR ratio (also expressed as percentage reduction relative to control group) along with the 95% confidence interval for the ARR ratio and the corresponding p-value will be obtained.

9.5.1.3 Time to first relapse

Analysis of time to first relapse will be done based on the FAS, using a Cox proportional hazard model with treatment, region (Japan or other countries), and baseline number of Gd-enhancing T1 weighted lesions (0 or ≥ 1) as factors, and number of relapses in previous year and baseline EDSS as covariates. The hazard ratio (also expressed as percentage reduction relative to control group) along with the 95% confidence interval for the hazard ratio and the corresponding p-value will be obtained.

In addition, Kaplan-Meier curves by treatment will be used to present the time-dependent cumulative frequency and percentage of subjects reaching the first relapse; by-treatment Kaplan-Meier estimates (with 95% confidence interval) at end of study will be obtained.

9.5.2 Safety variables (Core part)

Safety analyses will be conducted using the safety (SAF) dataset. Patients will be grouped by the actual treatment received. Safety data for the core part will be reported for the first time when the double-blind loading dose period has been completed by the last patient (data cut-off 1).

Unless explicitly otherwise stated, safety data will be reported up to and including the safety cut off of 30 days after permanent study drug discontinuation in patients who discontinued 30 days or more prior to cut-off 1, and up to cut-off 1 in all other patients.

The assessment of safety will be primarily based on the frequency of adverse events (including death and non-fatal serious adverse events). Additional safety assessments include laboratory tests, physical examination (including examination of skin), vital sign measures, ECG evaluations and assessment of suicidality. Clinically significant findings in these additional safety assessments will be reported as adverse events and analyzed as such. In addition all safety assessments will be summarized or listed as appropriate. The analyses of additional safety assessments will be defined on the level of the statistical analysis plan.

9.5.2.1 Adverse events

Treatment emergent adverse events (TEAE) will be reported up to and including safety cut off of 30 days after permanent study drug discontinuation in patients who discontinued 30 days or

more prior to cut-off 1, for all other patients TEAE will be reported up to cut-off 1. All serious TEAEs and death will be included, regardless of safety cut-off.

TEAEs will be summarized (number of cases as a percentage of number at risk) by treatment group. Number and percentage of patients with TEAE will be summarized by primary system organ class and preferred term. Serious TEAEs, drug related TEAEs and TEAEs leading to premature discontinuation from study drug will be presented in a similar format as adverse events. In addition, TEAEs will be reported by CTCAE grade.

9.5.2.2 Laboratory data

The summary of laboratory evaluations will be presented for 3 groups of laboratory tests: Hematology, Chemistry and Urinalysis.

Laboratory data will be summarized by presenting summary statistics of raw data and change from baseline values, and by presenting shift tables using clinically notable ranges (baseline to most extreme post-baseline value). Laboratory data, and specifically liver enzymes, will also be summarized by maximum change from baseline.

For liver enzymes, the number of subjects with newly occurring liver enzymes abnormalities will be summarized by treatment group. Newly occurring liver enzymes abnormalities are defined relative to the upper limit of normal (ULN). Example of a newly occurring liver enzyme event are ALT or AST $> 3 \times$ ULN & TBL $> 2 \times$ ULN & ALP $\leq 2 \times$ ULN or a reported Hy's Law case (refer also to [Appendix 1](#)).

Standardised MedDRA Queries (SMQ) and preferred terms searches for drug-related hepatic disorders will be conducted. Results of these searches will be analyzed and presented in a similar format as other adverse events. In case of liver events detailed listings will be provided.

In case of renal events, the overall frequency of events and percentage of patients with renal events during the treatment period will be summarized and detailed listings provided. Additional analyses of renal events can be defined in the statistical analysis plan.

9.5.2.3 Vital signs

Vital sign measurements and their change from baseline will be summarized with descriptive (mean, median, standard deviation, min, max) by visit. The number and percentage of subjects with clinically notable vital signs will be presented.

9.5.2.4 Suicidality evaluations

The Columbia Suicide Severity Rating Scale (CSSRS) data will be mapped to Columbia Classification Algorithm for Suicide assessment (C-CASA) as per Food & Drug Administration (FDA) guidance on suicidality.

The proportion of subjects who have completed suicide, suicide attempt, preparatory actions toward imminent suicidal behavior, suicidal ideation, and self-injurious behavior without suicidal intent as per the C-CASA scale during the study will be summarized by treatment group.

9.5.2.5 Other safety evaluations

All clinically significant safety findings based on additional safety evaluations (e.g. ECG or physical examination including assessments of skin, lymph nodes, lung, etc.) must be reported as adverse events on the CRFs capturing AEs. The statistical analysis of these findings will be done in the analysis of adverse events.

Other safety data will be summarized or listed as appropriate.

9.5.2.6 Safety evaluation during the Safety Follow-up period

Safety data collected during the Safety Follow-up period includes adverse events, laboratory assessments to measure B-cell repletion. All safety assessments after study drug discontinuation will be analyzed, summarized or listed.

[figure not shown]
Safety data collected during the Safety Follow-up period will be reported separately. These analyses will include laboratory assessments including B-cell repletion, adverse events, vital signs, MS relapses and change in EDSS. For all patients change is defined relative to the End of Study visit (EOS). Since post-treatment safety follow-up in the Safety Follow-up period may continue for up to 36 weeks (or longer if criteria for longer follow-up are met) after completion of the Treatment period study, the study report for the Core part (Screening and Double-blind treatment period) will be completed based on the completed core part i.e. based on all patients who have completed the Double-blind treatment period, and the partial data from the Safety Follow-up period available at that time. A complete analysis of the post-treatment safety follow-up will be provided in an addendum to the study report when all patients who entered the Safety Follow-up period have completed this period.

9.5.3 DNA

Not Applicable.

9.5.4 PK/PD

[figure not shown]
PK concentration and B-cell count data will be summarized by visit for the overall population, and separately by region (Japan or other countries) and provided together with by-patient listings in the study report.

9.5.5 Immunogenicity assessment

Samples will be analyzed for the presence of human anti-drug antibodies (ADA). The proportion of patients with ADA will be summarized by visit and overall (i.e. proportion of patients with ADA) as an assessment of the immunogenicity potential of ofatumumab. A listing by patient will also be provided.

9.7 Analysis of the Extension part

Analyses will include the combined data of the Core and Extension parts.

The extension FAS will include all available assessments of the Core and Extension parts. The main between-group comparisons of the efficacy variables will be based on the original randomization at the start of the Core part. The comparison will be between patients who were randomized to ofatumumab, and those who were initially randomized to placebo and received ofatumumab delayed, i.e. at the start of the Extension. Efficacy analyses will use similar models as described for the Core part of the study.

Extended safety and tolerability will be described by safety parameter summaries covering the whole period of continuous treatment with ofatumumab, i.e. by combining double-blind and open-label ofatumumab treatment. Placebo data will be excluded in this analysis. Details will be provided in the statistical analysis plan.

Details of analysis for the Extension part will be defined in a SAP document.

[figure not shown]
9.8 Interim analyses

No interim analysis will be conducted.

9.9 Sample size calculation

A total sample size of 60 patients, randomized 2:1 to ofatumumab and placebo, will provide more than **90% power** for a statistical test of superiority of ofatumumab compared with placebo at a one-sided alpha level 0.025. The power was calculated based on a negative binomial model under the assumption of 1.0 Gd-enhancing lesions per scan for placebo and a 92% relative reduction with ofatumumab (i.e. 0.08 Gd-enhancing T1 lesions per scan for ofatumumab), and a dispersion parameter $\kappa = 4.5$ (as observed in the combined Phase 3 placebo-controlled studies of fingolimod, namely FREEDOMS and FREEDOMS II studies for the same parameter, data on file). The sample size allows for a dropout rate of 10%.

Sample size calculation was done in EAST 6, version 6.3, Cytel Inc.

9.9.1 Evaluation of consistency in the treatment effect on the primary variable across regions

As a secondary objective the effect of ofatumumab on Gd-enhancing T1 lesion compared with placebo will be estimated for individual regions (Japan and other countries). It is planned to include 30 patients from Japan out of 60 in total.

The randomization will be stratified by region (Japan or other countries), and by Gd-lesion status on the screening scan (0 Gd-enhancing lesions or ≥ 1 Gd-enhancing lesions). Under the protocol assumptions for placebo, it is expected that approximately 2/3 of the patients will be free of Gd-enhancing lesions at baseline.

A simulation was performed to evaluate the consistency in efficacy on the primary variable across regions. Consistency is defined as a rate ratio < 1 in both Japan and other countries. For the simulation the following assumptions apply:

- The assumptions for the primary variable are the same for Japan and other countries and identical to those for the primary endpoint (i.e. 1 Gd-enhancing lesion per scan, a rate-ratio of 0.08 between ofatumumab and placebo, dispersion 4.5)
- In addition, it was assumed that the study would include 30 patients from Japan and 30 from other countries, and that patients would be randomized 2:1 to ofatumumab or placebo group in each region.

The probability to observe a consistent treatment effect between Japan and other countries was estimated to be higher than 99% under these settings.

Furthermore, we estimated the probability to observe a difference in treatment effect (percentage lesion reduction between ofatumumb and placebo) between Japan and other countries under the same assumptions. The probability to observe a difference of 20% or more (one-sided) in treatment effect between Japan and other countries was estimated to be $< 3\%$ (Table 9-1).

Table 9-1 Probability to observe a difference in Gd-lesion reduction across regions of more than delta

Delta*	Probability of a difference in percentage lesion reduction $>$ Delta
5%	13.7%
10%	6.1%
20%	2.3%
30%	1.3%

*Delta=Percentage lesion reduction for other countries - percentage lesion reduction for Japan

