9.4.2 Statistical model, hypothesis, and method of analysis

The null hypothesis is that there is no difference in the number of Gd-enhanced T1 weighted MRI lesions per scan between ofatumumab and placebo during the Core part. The alternative hypothesis is that there is a difference between the 2 treatment groups.

- Superiority of ofatumumab over placebo will be concluded if the mean number of Gd-enhanced T1 weighted MRI lesions per scan in patients treated with ofatumumab is lower compared with placebo and the observed p-value for the between-treatment comparison is less than the two-sided significance level of 0.05.

The null hypothesis will be tested on the FAS using a negative binomial regression model with log-link. Each patient's total number of Gd-enhanced T1 weighted MRI lesions during the Core part will be used as the response variable, and natural log of the number of MRI scans will serve as the offset variable to adjust for the different number of MRI scans between patients. The model will include treatment, region (Japan or other countries), and baseline number of Gd-enhanced T1 weighted lesions (0 or ≥ 1) as factors.

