9.4.3 Handling of missing values/censoring/discontinuations

The primary negative binomial model with an offset for the number of MRI scans adjusts for missing information (drop-out) under the assumption of non-informative drop-out, information is missing at random, and constant number of Gd-enhancing T1 weighted MRI lesions per scan within patient. Missing values will not be imputed. However, deviations from assumptions will be tested in sensitivity analyses.

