Furthermore, we estimated the probability to observe a difference in treatment effect (percentage lesion reduction between ofatumumab and placebo) between Japan and other countries under the same assumptions. The probability to observe a difference of 20% or more (one-sided) in treatment effect between Japan and other countries was estimated to be < 3% ([Table 3-1](#)).

Table 3-1 Probability to observe a difference in Gd-lesion reduction across regions of more than delta

Delta*	Probability of a difference in percentage lesion reduction > Delta
5%	13.7%
10%	6.1%
20%	2.3%
30%	1.3%

*Delta=Percentage lesion reduction for other countries - percentage lesion reduction for Japan

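### Protocol Table 9-1 (SAP Table 3-1) on regional differences cannot be obtained from the stated rate ratio of 0.08, and it understates chance differences at 5 and 10 points

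*Protocol*

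**What the plan says.** Protocol 9.9 bases the sample size on "1.0 Gd-enhancing lesions per scan for placebo and a 92% relative reduction with ofatumumab", with dispersion 4.5. Section 9.9.1 carries the same values into a regional simulation ("a rate-ratio of 0.08 between ofatumumab and placebo, dispersion 4.5"), with 30 patients from Japan and 30 from other countries, randomized 2:1 in each region.

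Two sets of results are reported:

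- Consistency, defined as a rate ratio below 1 in both regions: "The probability to observe a consistent treatment effect between Japan and other countries was estimated to be higher than 99% under these settings".
- The probability to "observe a difference in treatment effect (percentage lesion reduction between ofatumumb and placebo) between Japan and other countries under the same assumptions". Table 9-1 gives 13.7, 6.1, 2.3 and 1.3% for differences above 5, 10, 20 and 30 percentage points. The text summarises the 20-point row as below 3%.

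SAP 3.1 and Table 3-1 repeat the text and the figures unchanged.

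Neither document says whether 4.5 describes a single scan or the patient's four-scan total, which estimator the simulation used, or whether stratification on baseline lesions was simulated.

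**The concern.** The percentage reduction in each region is estimated from 10 placebo and 20 ofatumumab patients with highly overdispersed counts. With so few patients, chance differences of 5 or 10 points between regions should be common, and the printed 13.7% and 6.1% look too small.

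Regional consistency is the first-listed secondary objective of the Core part, and Protocol 3.2 ties it to registration in Japan. These probabilities are the only operating characteristics given for the 30 + 30 split. If they are too low, a reader could take an ordinary chance difference between regions as a sign of real inconsistency, or believe that 30 patients per region resolve the question better than they do.

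**Working it through.** **Inputs.** Protocol 9.9 and 9.9.1: 1.0 lesion per scan on placebo, rate ratio 0.08, dispersion 4.5, 20 ofatumumab and 10 placebo patients per region. Protocol 2.1.1: four scans. Mean totals per patient are therefore 4 × 1.0 = 4.0 and 4 × 0.08 = 0.32.

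**Method.** For n patients with negative binomial counts of mean μ and dispersion k, the sum is negative binomial with mean nμ and dispersion k/n. Regional totals have mean 10 × 4.0 = 40 on placebo and 20 × 0.32 = 6.4 on ofatumumab. The regional reduction is 1 − (ofatumumab mean / placebo mean), which is the maximum likelihood estimate without covariates. Delta is other countries minus Japan, one-sided, as in the table footnote. The unstratified rows at rate ratio 0.08 are exact enumerations.

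**What 4.5 could mean for the patient total.**
- If it applies to the total, k = 4.5. Two statements point this way: in Protocol 9.4.2 the patient's "total number of Gd-enhanced T1 weighted MRI lesions during the Core part will be used as the response variable", and Protocol 9.4.3 assumes a "constant number of Gd-enhancing T1 weighted MRI lesions per scan within patient", which carries between-patient variation from the scan to the total.
- If it applies per scan and scans within a patient are independent, the total has k = 4.5/4 = 1.125.
- The protocol's remark that "it is expected that approximately 2/3 of the patients will be free of Gd-enhancing lesions at baseline" fits mean 1 and dispersion 4.5 on one scan: (1 + 4.5)^(−1/4.5) = 0.685. It does not settle the correlation between scans.

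**Results (%).**

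| Setting | >5 | >10 | >20 | >30 | Both ratios <1 |
|---|---|---|---|---|---|
| Printed | 13.7 | 6.1 | 2.3 | 1.3 | >99 |
| 4.0 vs 0.32, k = 0 (Poisson) | 15.2 | 2.5 | 0.03 | 0.0 | 100 |
| k = 0.5 | 19.6 | 5.8 | 0.5 | 0.1 | 100 |
| k = 1.125 (independent scans) | 23.3 | 9.6 | 1.9 | 0.5 | 99.98 |
| k = 2.5 | 28.2 | 15.7 | 5.9 | 2.8 | 99.4 |
| k = 4.5, unstratified | 32 | 21 | 11 | 7 | 96.5 |
| k = 4.5, stratified on baseline lesions (simulated) | 30 | 17 | 7 | 3.5 | 99.2–99.4 |
| 4.0 vs 0.08 (ratio 0.02), k = 4.5 | 13.2–13.7 | 5.7–6.1 | 2.1–2.3 | 1.1–1.3 | 99.3–99.6 |

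The stratified row gives each patient one gamma rate (mean 1, dispersion 4.5) shared by the baseline scan and the four later scans, with blocks of 3 within region and baseline status. A crude ratio and a fitted negative binomial model with interaction and baseline status agree closely. The ranges in the last row reflect the handling of ties and of zero placebo counts.

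**Reading the table.**
1. The 5-point row is 15.2% without overdispersion and rises throughout the range from k = 0 to 4.5. The printed 13.7% lies below all of it. Allowing for 10% dropout (18 and 9 per region) raises the Poisson value to 16.4%.
2. The other rows would need different dispersions: 6.1% needs k = 0.54, 2.3% needs 1.28 and 1.3% needs 1.70. No single k gives the table.
3. The estimator is not the cause. A normal approximation on the log rate ratio with k = 4.5 has SE = √[(1/0.32 + 4.5)/20 + (1/4 + 4.5)/10] = 0.925 and gives 30.1/18.7/8.4/4.3%. With k = 0 the SE is 0.426 and the 5-point row is 15.5%.
4. A single scan, inverse dispersion, 40/20 per region, reversed or 1:1 allocation, two-sided counting, dropping zero counts and a continuity correction also failed to reproduce the table at ratio 0.08.
5. With 4.0 versus 0.08, counting differences at or above delta and keeping replicates with no placebo lesions, the rows are 13.66/6.13/2.34/1.29%, with 99.3% consistency.

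**Primary power.** With 40 and 20 patients, SE = √[(1/4 + 4.5)/20 + (1/0.32 + 4.5)/40] = 0.654. Then |ln 0.08|/0.654 − 1.96 = 2.526/0.654 − 1.96 ≈ 1.90, giving 97.1% power, or 95.6% with 36 and 18 patients. The stated power above 90% is reproduced.

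**The case against.** The strongest reply concerns scope. The consistency claim above 99% holds with independent scans (99.98%), with stratification modelled (99.2–99.4%) and under the log-scale approximation (99.4%). It fails only in the unstratified reading with total dispersion above about 3. The statement that 20 points or more has probability below 3% also holds with independent scans (1.9%), and the printed 30-point figure is then larger than the computed 0.5%. The arguments for applying 4.5 to the total come from the analysis model and the missing-data assumption, not from a description of the simulation. All of this stands. It limits which figures can be called wrong, but it does not rescue the 5- and 10-point rows, which are too low with 4.5 on either scale.

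The 5-point probability does not rise without limit: it peaks near 40% around k = 30 and falls to about 33% at k = 200. It never came near 13.7%, and such values are far from the stated 4.5.

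The pairing of 4.0 with 0.08 is an inference about a program that nobody outside the sponsor has seen, and the near-exact match depends on how ties and zero counts are treated. It should stay a lead to check.

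Finally, no decision rule uses the table. Consistency is to be judged from an interaction model, regional rate ratios with 95% confidence intervals and a forest plot at the Cut-off 1 analysis, so the actual uncertainty will be shown. The SAP history places that analysis before the current version, so a correction now amends the record of the planning justification. That keeps the point below a major one but does not make the printed figures right.

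**Conclusion.** The concern holds. At the stated rate ratio of 0.08, with four scans and 20 and 10 patients per region, no tested dispersion reproduces Table 9-1. The 5- and 10-point rows are too low under every reading of the stated 4.5: 23–32% instead of 13.7%, and 10–21% instead of 6.1%. If 4.5 applies to the patient total, the 20- and 30-point rows are also too low: 7–11% instead of 2.3%, and 3.5–7% instead of 1.3%.

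Confidence is high that the table does not follow from its stated inputs. The replacement values are less certain, because they depend on the level of the dispersion, the within-patient correlation and the treatment of stratification. The damage is confined to this planning justification. It should be fixed.

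**What to change.** Rerun the regional simulation with 1.0 versus 0.08 lesions per scan, that is 4.0 versus 0.32 over four scans. State whether 4.5 applies per scan or to the patient total, the within-patient correlation, the estimator, the handling of zero counts, and whether stratification on baseline lesions is simulated. Check whether the existing program paired a four-scan placebo total with a per-scan ofatumumab mean.

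Then restate all six figures (the consistency probability, the 20-point summary and the four rows) in Protocol 9.9.1 and SAP 3.1. With 4.5 on the total, expect about 96.5% consistency, 11% at 20 points and rows of 32/21/11/7% without stratification, or about 99%, 7% and 30/17/7/3.5% with it. Under independent scans the two summary claims would survive, but the rows would still change.

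The cost is one simulation run and text corrections in two documents, with less favourable planning figures as the result. No patients are added and no analysis changes.
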